#### 8.2.1.2. Assessment of Disease Response During Treatment

The first 2 disease assessments should be performed 6 and 12 weeks ( $\pm 7$  days) after the first dose of INCB099280 and axitinib and then Q12W ( $\pm 14$  days) thereafter (see Table 3). Imaging assessments may be performed more frequently if clinically indicated.

**Imaging should follow calendar days and should not be delayed for delays in cycle starts.**

Disease progression should be confirmed at least 4 weeks but less than 8 weeks after the first scan indicating disease progression in clinically stable participants as per guidelines in Section 6.6.8. A PET scan may be incorporated into the disease assessment to confirm progression per RECIST guidance. Participants who have unconfirmed disease progression may

continue on treatment until progression is confirmed, provided that they have met the conditions detailed in Section 6.6.8.

#### **8.2.1.3. Assessment of Disease Response After Treatment**

Participants who discontinue study treatment for a reason other than disease progression should continue to have efficacy assessments performed according to the original schedule following their final on-study treatment assessment until disease progression as determined by RECIST v1.1, new anticancer therapy is started, withdrawal of consent, lost to follow-up, death, or the end of the study, whichever occurs first.

#### **8.2.2. Medical Resource Utilization and Health Economics**

Medical resource utilization and health economics parameters are not evaluated in this study.

### **8.3. Safety Assessments**

See Section 6.6 for guidelines regarding the management of relevant laboratory or other safety assessment abnormalities.

#### **8.3.1. Adverse Events**

Adverse events will be monitored from the time the participant signs the ICF until at least 90 days after the last dose of study treatment or until the start of new anticancer therapy. Adverse events for enrolled participants that begin or worsen after informed consent should be recorded on the Adverse Events Form in the eCRF regardless of the assumption of a causal relationship with the study treatment. Conditions that were already present at the time of informed consent should be recorded on the Medical History Form in the eCRF. Adverse events (including laboratory abnormalities that constitute AEs) should be described using a diagnosis whenever possible rather than by individual underlying signs and symptoms.

Adverse events will be reported by the participant (or, when appropriate, by a caregiver or surrogate). The investigator and any qualified designees are responsible for detecting, documenting, and recording events that meet the definition of an AE or SAE and remain responsible for following up on AEs that are serious, that are considered related to the study treatment/procedures, or that caused the participant to discontinue the study treatment or withdraw from the study. Care will be taken not to introduce bias when detecting AEs and/or SAEs. Open-ended and nonleading verbal questioning of the participant, such as "How are you feeling?", is the preferred method to inquire about AE occurrences. Adverse events may also be detected when they are volunteered by the participant during the screening process or between visits or through physical examinations, laboratory tests, or other assessments. The definition, reporting, and recording requirements for AEs are described in Section 9.

All SAEs will be reported to the sponsor or designee by the investigator immediately without undue delay and not later than 24 hours of obtaining knowledge of the events. The investigator will also submit any updated SAE data to the sponsor immediately without undue delay and not later than 24 hours of obtaining knowledge of the update. After the initial AE/SAE report, the investigator is required to proactively follow each participant at subsequent visits/contacts. All SAEs will be followed until resolution, stabilization, the event is otherwise explained, or the participant is lost to follow-up (as defined in Section 7.3).

### 8.3.2. Vital Signs

Vital sign measurements (to be taken before blood collection for laboratory tests at the timepoints indicated in the SoA [see [Table 3](#)]) include BP, pulse, respiratory rate, and body temperature. If vital signs cannot be taken before blood collection for laboratory tests, there must be a minimum of 30 minutes from the completion of the blood collection procedures to the beginning of the vital signs collection. Blood pressure and pulse will be taken with the participant in a recumbent, semirecumbent, or sitting position after 5 minutes of rest (see [Section 6.6.6.1](#)).

Abnormal vital sign results identified after the first dose of study treatment constitute an AE if they are considered clinically meaningful, induce clinical signs or symptoms, require concomitant therapy, or require changes in study treatment.

### 8.3.3. Physical Examinations

Physical examinations must be performed by a medically qualified individual, such as a licensed physician, a physician assistant, or an advanced registered nurse practitioner, as local law permits. Abnormalities identified after the first dose of study treatment constitute an AE if they are considered clinically meaningful, induce clinical signs or symptoms, require concomitant therapy, or require changes in study treatment. Investigators should pay special attention to clinical signs related to previous serious illnesses. Physical examinations will be performed at the timepoints indicated in the SoA (see [Table 3](#)).

At the screening visit and EOT visit, a comprehensive physical examination should be conducted. The comprehensive physical examination will include height (at screening only) and weight and assessment(s) of the following organ or body systems: skin; head, eyes, ears, nose, and throat; thyroid; lungs; cardiovascular system; abdomen (liver, spleen); extremities; and lymph nodes; as well as a brief neurological examination.

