**Table 3: Schedule of Activities (Continued)**

Visit Day (Range)	Screening	Treatment				EOT (± 7 d)	Follow-Up			Notes
	Days –28 to –1	Cycles 1-2			Cycles 3+		Safety		Disease Status	
		Day 1	Day 8 (± 3 d)	Day 15 (± 3 d)	Day 1 (± 3 d)		EOT + 30 d (+ 7 d)	EOT + 90 d (+ 14 d)	Q12W (± 14 d) After EOT	
Administrative procedures (continued)										
Collect study drug and review dosing diary		X*	X	X	X	X				Section 6.4. *Cycle 2 only.
Assess compliance		X*	X	X	X	X				Section 6.4. *Cycle 2 only.
Clinical examination										
ECOG performance status	X	X			X	X	X			Section 8.3.4.
Vital signs	X	X	X	X	X	X	X	X		Section 8.3.2. Obtained prior to blood collection.
Physical examination	X*	X	X	X	X	X*	X	X		Section 8.3.3. *Comprehensive physical examination to be performed at screening and EOT visits only.
12-Lead ECG	X	X*			X†	X	X			Section 8.3.5. In the event that a single QTcF is > 480 ms at screening, the participant may enroll if the average QTc for 3 ECGs is ≤ 480 ms. *Collected predose and 2 and 4 hours postdose of INCB099280 and axitinib. †Collected predose beginning at Cycle 3 and then every third cycle (eg, Cycles 6, 9, 12, etc) until EOT and as clinically indicated.
Echocardiogram	X									Section 8.3.6. Additional assessments should be performed if clinically indicated.

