### **2.3.1. Clinical Experience With Axitinib Monotherapy**

Data from a randomized, multicenter, Phase 3 study directly comparing 2 VEGFR TKIs (axitinib and sorafenib) showed that inhibition of VEGFRs with axitinib translated into clinically meaningful efficacy with manageable toxicities in 361 participants with advanced RCC who had disease progression despite first-line therapy compared to sorafenib (n = 362; [Rini et al 2011](#)). The data also supported the hypothesis that biochemically more potent inhibition of the VEGFR

(as achieved with axitinib) produces a more robust clinical effect. On this basis, axitinib has been approved in the United Kingdom and European Economic Area as monotherapy for the treatment of adults with advanced RCC after failure of prior treatment with sunitinib or a cytokine.

The most frequent adverse effects or laboratory abnormalities (any Grade/Grade 3 or 4) associated with axitinib and reported in  $\geq 15\%$  of participants were diarrhea (55%/11%), creatinine elevation (55%/0%), hypertension (40%/16%), fatigue (39%/11%), hypocalcemia (39%/1%), anemia (35%/ $< 1\%$ ), decreased appetite (34%/5%), lymphopenia (33%/3%), nausea (32%/3%), dysphonia (31%/0%), palmar-plantar erythrodysesthesia and lipase elevation (27%/5%), weight decreased (25%/2%), vomiting (24%/3%), asthenia (21%/5%), constipation (20%/1%), hypothyroidism (19%/ $< 1\%$ ), arthralgia (15%/2%), cough as well as mucosal inflammation and stomatitis (15%/1% each), and thrombocytopenia (15%/1%). There were no treatment-related deaths, but there were 4 reported treatment-related or causality unknown deaths (asthenia, gastrointestinal bleed, sepsis, and disease progression).

One or more dose interruptions (due to missed doses or toxic effects) were reported in 77% of participants given axitinib; however, the median relative dose intensity was 99%. At least 1 dose reduction was reported in 31% of participants.

Although caution should be exercised when comparing across studies, a similar safety profile was observed in a randomized, open-label, Phase 3 study in which 192 participants with previously untreated advanced RCC received axitinib monotherapy compared to sorafenib ( $n = 96$ ; [Hutson et al 2013](#)).

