Treatment-emergent AEs (any Grade/Grade 3 or 4) reported in  $\geq 15\%$  of participants were diarrhea (54.3%/9.1%), hypertension (44.5%/22.1%), fatigue (38.5%/2.8%), hypothyroidism (35.4%/0.2%), decreased appetite (29.6%/2.8%), palmar-plantar erythrodysesthesia syndrome (28%/5.1%), nausea (27.7%/0.9%), ALT increased (26.8%/13.3%), AST increased (26.1%/7%), dysphonia (25%/0.2%), cough (21.2%/0.2%), constipation (20.7%/0%), arthralgia (18.2%/0.9%), weight decreased (17.7%/3%), proteinuria (17.5%/2.8%), dyspnea (16.1%/1.6%), headache (15.9%/0.9%), stomatitis (15.6%/0.7%), asthenia (15.2%/2.6%), and pruritus and stomatitis (15.5%/0.2% each).

Adverse events of any cause led to discontinuation of either drug in 30.5% of participants, discontinuation of both drugs in 10.7%, interruption of either drug in 69.9%, and dose reduction of axitinib in 20.3%. The median time to discontinuation of both pembrolizumab and axitinib because of AEs of any cause was 105.5 days, and the median time to discontinuation of pembrolizumab because of AEs of any cause was 65 days. Of the 11 participants (2.6%) who died from AEs, 4 (0.9%) died from treatment-related AEs (myasthenia gravis, myocarditis, necrotizing fasciitis, and pneumonitis in 1 participant each).

A similar safety profile was observed in 442 participants who received avelumab plus axitinib. Additionally, the frequency and severity of AEs observed with the combination treatment were generally consistent with the known safety profiles of avelumab and axitinib administered as monotherapy.

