**Table 4: Objectives and Endpoints**

Objectives	Endpoints
Primary	
To evaluate the safety and tolerability of INCB099280 in combination with axitinib (Part 1).	
 
• Occurrence of DLTs.
 
• Incidence of TEAEs, including assessment of physical examinations, changes in vital signs and ECGs, and analysis of clinical laboratory samples.
 
• Incidence of TEAEs leading to a dosing modification (treatment interruption, dose reduction, and permanent discontinuation of either study drug).
 

To assess the antitumor activity of INCB099280 in combination with axitinib (Part 2).	Objective response, defined as the best overall response of CR or PR by investigator assessment per RECIST v1.1.
Secondary	
To evaluate the safety and tolerability of INCB099280 in combination with axitinib (Part 2).	
 
• Incidence of TEAEs, including assessment of physical examinations, changes in vital signs and ECGs, and analysis of clinical laboratory samples.
 
• Incidence of TEAEs leading to a dosing modification (treatment interruption, dose reduction, and permanent discontinuation of either study drug).
 

To assess the antitumor activity of INCB099280 in combination with axitinib.	
 
• Objective response (Part 1), defined as the best overall response of CR or PR by investigator assessment per RECIST v1.1.
 
• Disease control, defined as the best overall response of CR, PR, or SD by investigator assessment per RECIST v1.1.
 
• DOR, defined as the time from the first CR or PR until disease progression by investigator assessment per RECIST v1.1 or death from any cause, whichever occurs earlier.
 

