#### **10.4.2.3. Vital Signs**

Descriptive statistics for the value at each assessment and change from baseline will be provided for vital signs (ie, BP, pulse, respiratory rate, and body temperature). Vital sign results will be reviewed for clinically notable abnormalities, and the abnormal values for participants exhibiting clinically notable vital sign abnormalities will be listed. Alert vital sign values are defined as an absolute value outside the defined range and an absolute percentage change of > 25% from baseline. The abnormal values for participants exhibiting alert vital sign abnormalities will be listed.

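### Body weight is required only at screening and EOT, so detecting, grading and dating weight loss on treatment depends on unscheduled, site-dependent weighing

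*Protocol*

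**What the plan says.** Weight enters the protocol's schedule through the comprehensive physical examination alone. Section 8.3.3 says "At the screening visit and EOT visit, a comprehensive physical examination should be conducted", and on its content: "The comprehensive physical examination will include height (at screening only) and weight and assessment(s) of the following organ or body systems". The note to the physical examination row of Table 3 confirms the timing: "Comprehensive physical examination to be performed at screening and EOT visits only". A physical examination is also marked at every treatment visit and at both safety follow-up visits, but its content there is not defined.

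Weight is not a vital sign. In Section 8.3.2 the measurements "include BP, pulse, respiratory rate, and body temperature". The planned summaries in Section 10.4.2.3 cover the same four items: "vital signs (ie, BP, pulse, respiratory rate, and body temperature".

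The protocol's own background names the event as common. Section 2.3.1 cites weight decreased in 25% of participants on axitinib alone (2% Grade 3 or 4). Section 2.3.2 cites 17.7% (3% Grade 3 or 4) with axitinib plus pembrolizumab. Both figures come from renal cell carcinoma studies.

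The endpoint concerned is primary in Part 1 and secondary in Part 2 (Table 4): "Incidence of TEAEs, including assessment of physical examinations, changes in vital signs and ECGs, and analysis of clinical laboratory samples". It is an incidence. Section 10.4.2.1 counts events from the first dose to 90 days after the last dose, or to new anticancer therapy if earlier. INCB099280 may be given for up to 35 cycles of 21 days.

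**The concern.** Weight loss is a gradual, measured sign. To grade it, one needs a baseline and a current weight; to date it, one needs weights in between. The plan names it as a frequent effect of one of the two study drugs but fixes no measurement between the two ends of treatment. Section 9.3 asks for each change in severity to be recorded as a separate event, and the scheduled data cannot show such changes for weight.

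At stake is how complete and comparable one adverse event term is within the TEAE endpoint. A site that weighs participants at every visit and one that does not would report different rates from the same patients. A loss that develops and recovers before EOT has no required measurement that would show it. A later statistical analysis plan cannot repair this, because weights that were not collected cannot be analysed.

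**Working it through.** The protocol gives no figure of its own to reproduce here. The check is a reading of the schedule plus simple counts.

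1. **Visits without a required weight (Table 3).** Cycles 1 and 2 have Days 1, 8 and 15: 2 × 3 = 6 visits. Cycles 3 to 35 have Day 1 only: 35 − 2 = 33 visits. Total: 6 + 33 = 39 treatment visits for a participant who completes 35 cycles. Each carries a physical examination and an adverse event assessment; none requires a weight. The visits 30 and 90 days after EOT do not require one either, though both can fall in the TEAE window.

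2. **Longest gap between the two required weights.** Treatment lasts at most 35 × 21 = 735 days. Adding up to 28 days of screening and the 7-day EOT window gives 28 + 735 + 7 = 770 days. This is a maximum; most participants will stop sooner.

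3. **Baseline.** No weight is required on Cycle 1 Day 1, so the last required pre-dose weight can be up to 28 days old. A change between screening and first dose cannot then be separated from a change on treatment.

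4. **How common the event might be.** Assume the renal cell carcinoma rates carry over and every event is found.
   - Part 1, 12 participants: 12 × 0.25 = 3.0; 12 × 0.177 = 2.1.
   - One Part 2 cohort of 30: 30 × 0.25 = 7.5; 30 × 0.177 = 5.3. Grade 3 or 4: 30 × 0.02 = 0.6; 30 × 0.03 = 0.9.

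   These are expected events, not missed events.

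5. **What incomplete detection would do.** Observed rate = true rate × detection sensitivity. The document gives no sensitivity, so the values below are assumptions that only show the range.

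| Assumed sensitivity | Observed, if true rate is 25% | Observed, if true rate is 17.7% |
|---|---|---|
| 50% | 12.5% | 8.85% |
| 70% | 17.5% | 12.4% |
| 90% | 22.5% | 15.9% |

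The spread follows entirely from the assumed column. It shows that the loss cannot be sized from the document, not that it is large.

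**The case against.** The best defence is that detection does not rest on the scale alone. A physical examination and adverse event questioning take place at every treatment visit. Section 8.3.1 allows events to be found through examinations or other assessments, and Section 8.7 provides for unscheduled visits. The content of the interim examinations is open, so weighing is not excluded. All of this stands. It means that under-detection is a risk of unknown size, not an established fact; it does not turn an optional measurement into a required one.

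It is also fair that timing does not alter an incidence endpoint. The EOT weight lies within the TEAE window unless new therapy has begun, so a loss still present then is measured and counts if the investigator judges it an adverse event. No two passages contradict each other.

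Several stronger readings are tempting and not supported:

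- A reader might take 132 × 0.177 = 23 to 132 × 0.25 = 33 participants as the size of the defect. Those are events expected at the cited rates. How many would go unseen is unknown.
- A reader might divide the estimated 12 months of participation by 21 days and speak of 17 unweighed cycle visits. The 12 months include screening and follow-up. Removing 28 and 90 days leaves 365 − 118 = 247 days, or 247/21 ≈ 12 cycles.
- A reader might infer that the mg/kg steroid doses in Table 11 would rest on the screening weight. The protocol does not say which weight is used, and nothing prevents weighing at that moment.
- A reader might infer that dose finding suffers, since the general Grade 3 or higher item in Table 8 could in principle take in severe weight loss. The protocol gives no rate for the 21-day DLT period, and examinations are scheduled on Days 1, 8 and 15. Nothing supports that claim.

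**Conclusion.** The point holds as a gap in the fixed schedule of measurements. The protocol requires weight at screening and EOT only, omits it from vital signs in both the assessment and analysis sections, and cites weight decreased as frequent with axitinib. Between those visits, detection, worst grade and onset rest on unscheduled weighing that may differ by site. Loss that recovers before EOT may be missed.

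The schedule facts need no assumption. The relevance rests on the cited renal cell carcinoma rates applying roughly to gynecological cancers. The number of missed events cannot be computed. The objective response rate, the DLT rules, the futility threshold and the sample size are untouched. This is a cheap improvement to one term of the safety endpoint, not an error that endangers the trial's conclusions.

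**What to change.** In Table 3 and Section 8.3.2, add body weight on Day 1 of every cycle and at the visit 30 days after EOT. Take the Cycle 1 Day 1 weight before the first dose and use it as baseline. Keep the screening and EOT weights. The vital signs row of Table 3 is also marked on Days 8 and 15 and at 90 days after EOT, so give weight its own row or a footnote naming its visits.

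In Section 10.4.2.3, add weight to the summaries of value and change from baseline, and state whether the alert rule there (outside the range and more than 25% change) is meant to apply to it.

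The cost is one short measurement and one eCRF field at visits that already take place: at most 35 + 1 = 36 added weighings for a participant who completes 35 cycles. No new visit is needed. The change should be made early, because missed weights cannot be recovered.

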### 8.3.4. Eastern Cooperative Oncology Group Status

The ECOG performance status score will be assessed as outlined in [Table 3](#) and according to the criteria in [Table 16](#).

**Table 16: Eastern Cooperative Oncology Group Performance Status Scoring**

Grade	ECOG Performance Status
0	Fully active, able to carry on all predisease performance without restriction
1	Restricted in physically strenuous activity but ambulatory and able to carry out work of a light or sedentary nature, eg, light house work, office work
2	Ambulatory and capable of all self-care but unable to carry out any work activities; up and about more than 50% of waking hours
3	Capable of only limited self-care; confined to bed or chair more than 50% of waking hours
4	Completely disabled; cannot carry on any self-care; totally confined to bed or chair
5	Dead

Source: [Oken et al 1982](#).

### 8.3.5. Electrocardiograms

Single 12-lead ECGs will be obtained as outlined in [Table 3](#) and [Table 17](#) using a local ECG machine that automatically calculates the heart rate and measures PR, QRS, QT, and QTcF intervals. All 12-lead ECGs will be performed with the participant in a recumbent or semirecumbent position after 5 minutes of rest.

The 12-lead ECGs will be interpreted by the investigator at the site to be used for immediate participant management. Additional 12-lead ECGs may be performed as clinically indicated to manage participant safety. The decision to include or exclude a participant or discontinue study treatment based on an ECG flagged as "Abnormal, Clinically Significant" is the responsibility of the investigator, in consultation with the sponsor's medical monitor as appropriate. Clinically notable abnormalities that are considered clinically significant in the judgment of the investigator are to be reported as AEs. The Fridericia correction method for calculating QTc will be used and recorded in the eCRF.

In the event that a single QTcF is  $> 480$  milliseconds at screening, the participant may enroll if the average QTc for 3 ECGs is  $\leq 480$  milliseconds.

**Table 17: Timing of Electrocardiograms**

Study Visit	Timing of Collection			
	Any Time	Before the Morning Dose of INCB099280 and Axitinib a	2 Hours After the Morning Dose of INCB099280 and Axitinib b	4 Hours After the Morning Dose of INCB099280 and Axitinib b
Screening	X			
Cycle 1 Day 1		X	X	X
Cycle 2 Day 1		X	X	X
Cycle 3 Day 1 and Day 1 of every third cycle (eg, Cycles 6, 9, 12, etc) thereafter		X		
EOT	X			
Safety follow-up	X			

a INCB099280 and axitinib are administered in the clinic on days of timed ECGs.

b To be collected within 15 minutes before blood draws. Electrocardiogram measurements should be aligned with timing of PK blood draws.

